##### **9.4.2. Primary and Secondary Endpoint analysis**

For the primary efficacy endpoint, the proportion of insulin-independent patients over the time frame of day 365 $\pm$ 14 after the transplant, the differences in proportions will be assessed using the Pearson Chi-square statistic, stratified by the three groups at baseline: < 2500 IEQ/kg vs. 2500-5000 IEQ/kg vs. > 5000 IEQ/kg. The significance level used for statistical testing will be 2.5% and one-sided test will be used. The 95% confidence interval for treatment proportions and for the difference in treatment proportion between reparixin and placebo will be produced. The primary analysis will be performed using both ITT population with PP analysis serving as a sensitivity analysis.

For secondary endpoints that will be tested both at 75 $\pm$ 14 and 365 $\pm$ 14 days after the transplant, only the day 365 $\pm$ 14 time point will be tested for superiority in the fixed sequence testing procedure.

The C-peptide AUC after the MMTT normalized by IEQ/kg will be analyzed at the two time points by a repeated measurements model using PROC MIXED within SAS®, including terms for treatment, time point and center. The treatment effect within each time point will be compared using a two-sided test at the 5% level. The estimated treatment difference between reparixin and placebo at each time point will be presented together with the corresponding 95% confidence interval. The confidence interval will be generated using  $\alpha=0.05$ .

The mean in average daily insulin requirements at the two time points will be analyzed using a repeated measurements model using PROC MIXED within SAS®. The model will include fixed effect

terms for center, time point and treatment. Time point will be specified as a repeated measurement. The treatment effect within each time point will be compared using a two sided test at the 5% level.

The proportion of patients with an HbA1c  $\leq 6.5\%$  will be analyzed at day  $365 \pm 14$ . Additionally, the proportion of patients with an HbA1c  $\leq 6.5\%$  at day  $365 \pm 14$  will be analyzed again, but patients are included in this second analysis if they are also free of severe hypoglycemic events from day  $75 \pm 14$  to day  $365 \pm 14$  inclusive. Treatment effect will be analyzed using Pearson Chi-square.

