## 7.3 Methods for Multiplicity Correction in Analyses

If the primary analysis of the primary endpoint leads to rejection of the null hypothesis, the null hypotheses for the following secondary endpoints will be tested in a conditional sequential manner. The sequence in which these secondary endpoints will be tested is as follows:

1. AUC for serum C-peptide level during the first 4 hours of a MMTT, normalized by the number of IEQ/kg, at Day 365 ± 14 days after IAT.
2. Average daily insulin requirement at Day 365 ± 14 days after IAT.
3. Time course of C-peptide derived from the MMTT at Day 365 ± 14 days after IAT.
4. β-cell function as assessed by β-score at Day 365 ± 14 days after IAT.
5. The proportion of patients with HbA1c ≤ 6.5% at Day 365 ± 14 days after IAT.

REP0112

Statistical Analysis Plan

6. Cumulative number of severe hypoglycemic events from Day 75 ± 14 days to Day 365 ± 14 days after IAT.
7. The proportion of patients with HbA1c ≤ 6.5% at Day 365 ± 14 days after IAT **AND** free of severe hypoglycemic events from Day 75 ± 14 days to Day 365 ± 14 days after IAT, inclusive.

A null hypothesis will be rejected if and only if the primary analysis of that endpoint and all primary analyses of preceding primary and secondary endpoints result in a rejection of the respective null hypotheses. This procedure protects the family-wise false positive error rate at the overall one-sided 0.025 level.

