## 7.5.2 Secondary Variables

### 7.5.2.1 Area Under the Curve for C-peptide During First 4 Hours of a Mixed Meal Tolerance Test

C-peptide is to be collected at 9 time points (2 basal measurements and at 15, 30, 60, 90, 120, 180, and 240 minutes) during the first 4 hours of a mixed meal tolerance test on both Days 75 and 365 after IAT. For both Days 75 and 365, the area under the curve normalized by IEQ/kg infused during IAT will be computed as described in Section 5 of this SAP. AUC values at each day will be summarized descriptively by treatment group.

Analysis will be performed in two steps. First, the AUC normalized by IEQ/kg infused during IAT at each day will be compared between treatment groups using the t-test (two-sided tests at the 5% level of significance).

Second, the AUC normalized by IEQ/kg infused during IAT at the two days will be analyzed by a repeated measurements model using PROC MIXED within SAS®. The model will include fixed effect terms for site, time (Days 75 and 365), and treatment. Time will be specified as a repeated measurement. In order to select an appropriate matrix for the observations within each patient, 3 models will be fitted using the compound symmetry, Huynh-Feldt, and unstructured covariance structures. The matrix for the final model will be selected using Akaike's Information Criterion where the lowest value indicates the best fit. Type III sums of squares from the mixed procedure within SAS® will be used to assess the significance of individual terms within the model using the selected matrix structure. The importance of the treatment-by-site interaction will be investigated and if the term is not significant at the 0.10  $\alpha$ -level, it will be excluded from the model. A logarithmic transformation of the data will be considered if found to be more suitable.

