## REP0112

## Statistical Analysis Plan

The adjusted least squares means and associated 95% confidence intervals will be estimated for each combination of day and treatment, and the adjusted least squares mean difference (reparixin minus placebo) and associated 95% confidence interval at each day will also be estimated. The treatment effect within each day will be tested using a two-sided test at the 5% level. The tests of the fixed effects in the model will also be presented.

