#### 7.6.2.2 Post-transplant Safety Laboratory Parameters

Post-transplant safety laboratory parameters to be summarized include the following.

- AST, ALT, INR, PTT, fibrin degradation products, and C-reactive protein.

Samples for post-transplant safety laboratory parameters are taken at Days 1 through 7 post-transplant and on Day 75 ± 14 days for AST and ALT. Each parameter will be summarized descriptively at each applicable time point by treatment group and in total.

Change from baseline (screening) at each applicable follow-up time point will be summarized for AST and ALT by treatment group and in total. Change from baseline (screening) will be analyzed within a single repeated measurements model (for each of AST and ALT) using PROC MIXED within SAS®. The model will include fixed effect terms for site, time (Days 1 through 7 and 75), and treatment; the treatment by time interaction; the treatment by study site interaction if significant at the 0.10  $\alpha$ -level; baseline value as a covariate; and a random effect for patient. A compound symmetry covariance structure will be used to account for the multiple observations from the same patient.

The adjusted least squares means and associated 95% confidence intervals will be estimated for each combination of day and treatment, and the adjusted least squares mean difference (reparixin minus placebo) and associated 95% confidence interval at each day will also be estimated. The treatment effect within each day will be tested using a two-sided test at the 5% level. The tests of the fixed effects in the model will also be presented.

Observed values for all parameters will also be presented as box plots for each treatment group at each time point.

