## 3 STATISTICAL METHODS

### 3.1 Methods for Multiplicity Correction in Analyses

All efficacy endpoints planned in this addendum are exploratory in nature and will be tested without a multiplicity correction being applied. In addition, all efficacy endpoints planned in the SAP will also be interpreted without the planned conditional sequential multiplicity correction being applied.

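### The C-peptide AUC and daily-insulin mixed models have no treatment-by-time term, so their Day 75 and Day 365 treatment differences are one and the same number

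*SAP*

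**What the plan says.** SAP 7.5.2.1 (C-peptide AUC normalised by IEQ/kg) and 7.5.2.2 (average daily insulin requirement) use the same two steps.

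- Step one: the endpoint "at each day will be compared between treatment groups using the t-test".
- Step two: a PROC MIXED repeated-measures model. "The model will include fixed effect terms for site, time (Days 75 and 365), and treatment". Treatment-by-site is kept only if significant at 0.10. Three covariance structures are fitted (compound symmetry, Huynh-Feldt, unstructured), and "The matrix for the final model will be selected using Akaike's Information Criterion where the lowest value indicates the best fit".
- Output of step two: least squares means for each day and arm, and a difference with 95% interval at each day. "The treatment effect within each day will be tested using a two-sided test at the 5% level".

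Protocol 9.4.2 describes the AUC model in the same way, "including terms for treatment, time point and center", and also asks for the treatment effect within each time point.

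Other models in the same documents do name the missing term. SAP 7.6.2.2 (ALT/AST) lists "the treatment by time interaction", and so does SAP 7.6.3 for weight, on the same two days. The addendum's shell footnotes for un-normalised AUC and for insulin requirement stratified by IEQ/kg also include it. Yet Addendum 3.2.2.1 and 3.2.2.2 say those analyses follow the SAP models.

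SAP 7.3 makes each secondary test depend on "the primary analysis of that endpoint and all primary analyses of preceding primary and secondary endpoints", without saying whether the t-test or the model is that analysis. Addendum 3.1 later states that "all efficacy endpoints planned in the SAP will also be interpreted without the planned conditional sequential multiplicity correction being applied".

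**The concern.** The requested output needs a treatment effect that can differ between Day 75 and Day 365, and the stated model does not allow one. Declaring time as a repeated measurement sets the covariance of a patient's two values, not the means.

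The figures labelled Day 365 would therefore not describe Day 365. In most settings an effect that fades by one year is overstated and one that appears late is diluted. The mix of days is not fixed in advance either, because it depends on the covariance structure that Akaike's criterion picks. The t-test and the model could disagree at Day 365 with no rule on which counts. One of the two endpoints, normalised AUC, is called the key secondary endpoint in SAP 3.3.

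**Working it through.** **1. The plan's own figure.** SAP 3.3 gives more than 95% power for normalised AUC with 52 per arm, difference 1.48, SD 1.37 and two-sided alpha 0.0025. Here 1.48 / (1.37 × √(2/52)) = 5.51, which gives power 0.994 (normal) or 0.991 (noncentral t). The figure is reproduced. It concerns one comparison of means, so it does not bear on the two-day model.

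**2. The identity.** With mean = intercept + site + time + β × treatment, reparixin minus placebo at either day is β, because the site and time terms cancel. This holds for every listed covariance structure, with missing data, and if treatment-by-site is kept. In simulated data the largest gap between the two days' estimates was 0.0.

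**3. What β estimates.** With complete data, SDs s75 and s365, correlation r and n per arm:

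- Day 365 weight w = (s75² − r·s75·s365) / (s75² + s365² − 2r·s75·s365)
- Variance = (2/n)·s75²·s365²·(1 − r²) / (s75² + s365² − 2r·s75·s365)
- Estimate = (1 − w) × Day 75 effect + w × Day 365 effect
- Rejection in the direction of the effect = 1 − Φ(1.96 − estimate/SE), the favourable half of the two-sided 5% test

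Compound symmetry fixes w at 0.50; the unstructured matrix uses the estimated variances. With SDs 1.0/1.37 and r = 0.5, w is 0.50 under compound symmetry and 0.209 under unstructured.

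**4. Size.** Assumptions, none from the documents: n = 50 per arm, complete data, r from 0.3 to 0.8, effects in SDs of the day concerned. The 1.37 ratio is illustrative only.

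Worked case (equal SDs, r = 0.5, 0.5 SD at Day 75 and 0 at Day 365): w = 0.50, estimate 0.25, variance 0.04 × 0.75 = 0.03, SE 0.173, ratio 1.44, rejection 30%.

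| SD Day 75 / Day 365 | w, r = 0.3 to 0.8 | 0.5 SD at Day 75 only: rejection at Day 365 (nominal 2.5%) | 0.6 SD at Day 365 only: power (85% for a Day 365 contrast) |
|---|---|---|---|
| 1.0 / 1.0 | 0.50 | 34% to 26% | 46% to 35% |
| 1.0 / 1.37 | 0.29 to −0.14 | 50% to 82% | 25% to 1% |
| 1.37 / 1.0 | 0.71 to 1.14 | 19% to 1% | 65% to 93% |

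Milder case, equal SDs, 0.6 SD at Day 75 fading to 0.3 SD: the reported Day 365 estimate is (0.6 + 0.3)/2 = 0.45 SD, 50% too large. It is significant in 80% to 66% of trials, against 32% for a true Day 365 contrast.

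**5. Simulation, unstructured covariance estimated** (300 trials each, r = 0.5), rejection without versus with treatment-by-time:

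- equal SDs, 0.5 SD at Day 75 only: 31% versus 2.3%
- equal SDs, 0.6 SD at Day 365 only: 43% versus 83%
- SDs 1.0/1.37, 0.5 SD at Day 75 only: 53% versus 2.3%
- SDs 1.37/1.0, 0.5 SD at Day 75 only: 9% versus 2.3%

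**6. Simulation with the plan's planning values** (52 per arm, SD 1.37, 9 sites; assumed r of 0.3, 0.5 and 0.7, 10% missing at Day 365, known compound symmetry; 400 trials each, two-sided 5%):

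- True effects 1.48 at Day 75 and 0 at Day 365: both days report 0.77 to 0.82. Day 365 is rejected in 88% to 90% of trials, against 4% to 7% with the term.
- True effects 0 and 1.48: both days report 0.68 to 0.69. Day 365 power is 74% to 86%, against 99.8% to 100%.

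**The case against.** The strongest reply is that the term list was not meant to be complete. The same paragraph adds treatment-by-site, and least squares means for each day and arm make little sense unless treatment-by-time is fitted. The addendum shells, said to follow the SAP model, print that term. This makes a drafting omission likely. It does not correct the text behind the main AUC and insulin tables, and the SAP does write the term out for ALT/AST and weight.

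The consequence is also limited, and this stands. The step-one t-tests give a valid Day 365 comparison, the primary endpoint is untouched, and Addendum 3.1 removes the sequential testing. Identical results on both days would be visible in the output. But the model-based figures would still carry the wrong label, and nothing says which Day 365 result counts.

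The scenarios are illustrative, and two of the three put the whole effect on one day. If the effect is the same at both days, the model as written is unbiased and more powerful: at 0.5 SD, equal SDs and r = 0.5, about 82% against 71% for a single-day contrast. That gain comes from Day 75 data, which a Day 365 claim cannot properly use. Overstatement of a fading effect is not universal: with SDs 1.37/1.0 and r = 0.8 the Day 75 weight is −0.14 and the effect is understated.

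**Conclusion.** The concern holds and should be fixed. That the two days share one estimate, interval and p-value is algebra and needs no assumption. The size depends on how far the effect differs between days, the two SDs and the within-patient correlation, none of which the documents give. With equal SDs and 50 per arm, false Day 365 findings from an effect of 0.5 SD confined to Day 75 run at roughly ten to fourteen times the nominal 2.5%, and power for an effect of 0.6 SD confined to Day 365 is about half what it should be.

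SAP 7.5.2.3 (MMTT time courses) is affected less. It models each visit day separately, so its overall Day 365 treatment test remains a Day 365 result. There the missing treatment-by-minute term only makes every per-time-point contrast equal the overall effect.

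**What to change.** - Add treatment-by-time to the models in SAP 7.5.2.1 and 7.5.2.2, and report the Day 365 contrast from them.
- Before database lock, name either that contrast or the Day 365 t-test as the primary analysis of each of the two endpoints.
- In SAP 7.5.2.3 add treatment-by-minute, and keep the overall treatment test as its Day 365 result.
- Record the added term in SAP 1.2 as a change from Protocol 9.4.2.

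The cost is SAP wording and one model term per section. No further data are needed. The precision from pooling the two days is given up.

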## REP0112

## Statistical Analysis Plan

The adjusted least squares means and associated 95% confidence intervals will be estimated for each combination of day and treatment, and the adjusted least squares mean difference (reparixin minus placebo) and associated 95% confidence interval at each day will also be estimated. The treatment effect within each day will be tested using a two-sided test at the 5% level. The tests of the fixed effects in the model will also be presented.

#### 7.5.2.2 Average Daily Insulin Requirements

The average daily insulin requirement (ADIR) will be computed by site personnel using data from the patient diary card and reported on Pages 24 and 24.1 for Days 75 and 365, respectively. ADIR values at each day will be summarized descriptively by treatment group.

ADIR will be analyzed in two steps as done for AUC of C-peptide. First, ADIR at each day will be compared between treatment groups using the t-test (two-sided tests at the 5% level of significance). Second, ADIR at Day 75 and Day 365 will be analyzed as repeated measures with a single repeated measurements model using PROC MIXED within SAS®. The model will include fixed effect terms for site, time (Days 75 and 365), and treatment. Time will be specified as a repeated measurement. In order to select an appropriate matrix for the observations within each patient, 3 models will be fitted using the compound symmetry, Huynh-Feldt, and unstructured covariance structures. The matrix for the final model will be selected using Akaike's Information Criterion where the lowest value indicates the best fit. Type III sums of squares from the mixed procedure within SAS® will be used to assess the significance of individual terms within the model using the selected matrix structure. The importance of the treatment-by-site interaction will be investigated and if the term is not significant at the 0.10  $\alpha$ -level, it will be excluded from the model. A logarithmic transformation of the data will be considered if found to be more suitable.

The adjusted least squares means and associated 95% confidence intervals will be estimated for each combination of day and treatment, and the adjusted least squares mean difference (reparixin minus placebo) and associated 95% confidence interval at each day will also be estimated. The treatment effect within each day will be tested using a two-sided test at the 5% level. The tests of the fixed effects in the model will also be presented.

#### 7.5.2.3 Time Course of Glucose, C-peptide, and Insulin

Glucose, C-peptide, and insulin are to be collected at 9 time points (2 basal measurements and at 15, 30, 60, 90, 120, 180, and 240 minutes) during the first 4 hours of a mixed meal tolerance test on both Days 75 and 365 after IAT.

The time course of each of these parameters at Days 75 and 365 will be analyzed separately with a repeated measurements model using PROC MIXED within SAS®. Each repeated measures model will include fixed effect terms for site, time (the average of 2 basal measurements at time 0 and at 15, 30, 60, 90, 120, 180, and 240 minutes), and treatment. Time will be specified as a repeated measurement. In order to select an appropriate matrix for the observations within each patient, 3 models will be fitted using the compound symmetry, Huynh-Feldt, and unstructured covariance structures. The matrix for the final model will be selected using Akaike's Information Criterion where the lowest value indicates the best fit. Type III sums of squares from the mixed procedure within SAS® will be used to assess the significance of individual terms within the model using the selected matrix structure. The importance of the treatment-by-site interaction will be investigated and if the term is not significant at the 0.10  $\alpha$ -level, it will be excluded from the model. A logarithmic transformation of the data will be considered if found to be more suitable.

Separately for each day (Day 75 and Day 365), parameter values at each time point will be summarized descriptively by treatment group. The adjusted least squares means and associated 95% confidence intervals will be estimated for each combination of time and treatment, and the adjusted least squares mean difference (reparixin minus placebo) and associated 95% confidence interval at each time will also be estimated. The treatment effect within each time will be tested using a two-sided test at the 5% level. Adjusted least squares means for each treatment and the treatment effect, associated 95% confidence intervals, and a two-sided p-value testing treatment effect over all time points at the 5% level will also be presented. The tests of

REP0112

Statistical Analysis Plan

the fixed effects in the model will also be presented. The time course of adjusted least squares means for each parameter will be plotted over time.

Separately for each day (Day 75 and Day 365), the peak (maximum) C-peptide and time to peak C-peptide value will be summarized descriptively. The time to peak value in minutes will be computed as the time of the peak value (HH:MM on a 24-hour clock) minus the end time of the mixed meal (HH:MM on a 24-hour clock) as recorded on the mixed meal tolerance test CRF.

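### SAP 7.5.2.3 leaves treatment-by-time out of the MMTT time-course models, so the overall p-value is weighted by whichever covariance AIC selects and the required per-time differences cannot differ

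*SAP*

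**What the plan says.** SAP 7.5.2.3 covers the glucose, C-peptide and insulin courses, modelled separately for Day 75 and Day 365. The fixed effects are given as follows: "Each repeated measures model will include fixed effect terms for site, time (the average of 2 basal measurements at time 0", followed by the post-meal samples ending "90, 120, 180, and 240 minutes), and treatment. Time will be specified as a repeated measurement". That makes eight time levels and no treatment-by-time term.

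The covariance is not fixed in advance: "3 models will be fitted using the compound symmetry, Huynh-Feldt, and unstructured covariance structures", and "The matrix for the final model will be selected using Akaike's Information Criterion where the lowest value indicates the best fit". The scale is also open: "A logarithmic transformation of the data will be considered if found to be more suitable".

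The same section requires LS means for every time-and-treatment cell, a treatment difference with confidence interval at each time, and a two-sided 5% test at each time. It then adds an overall test: "a two-sided p-value testing treatment effect over all time points at the 5% level will also be presented".

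The endpoint "Time course of C-peptide derived from the MMTT at Day 365 ± 14 days after IAT" is third among the secondary endpoints in SAP 7.3. Addendum 3.1 later withdraws the sequential multiplicity correction for all efficacy endpoints.

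**The concern.** The listed terms and the required outputs do not fit together. A model with one treatment coefficient has the same estimated difference at fasting, at 90 minutes and at 240 minutes, so separate per-time differences and tests do not exist in it.

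The overall p-value is affected too. Without the interaction, the treatment estimate is a generalized least squares average of the eight time-specific differences. The weights come from the covariance matrix, not from the clinical question. If the fasting sample has the smallest variance and is well correlated with later samples, it can take most of the weight, and some stimulated samples can be subtracted.

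The drug is meant to preserve islet function, so a benefit could well show as a proportional rise or a larger meal response rather than a constant shift. The overall p-value could then miss the effect or point the wrong way. It is the only single p-value that section 7.5.2.3 offers for the third secondary endpoint.

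**Working it through.** **Plan figures.** The documents state no power, SD or correlation for the time course, so there is nothing to reproduce directly. The nearest figure is the AUC power in SAP 3.3: 52 per arm, difference 1.48, SD 1.37, two-sided alpha 0.0025. SE = 1.37 × √(2/52) = 0.269; 1.48/0.269 = 5.51; power = Φ(5.51 − 3.02) = 99.4%. This agrees with the stated figure of more than 95%, but says nothing about weights.

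**Formula.** With S the 8 × 8 within-patient covariance, the no-interaction estimate is Σ wᵢ dᵢ, with w = S⁻¹1 / (1′S⁻¹1). With treatment-by-time in the model, the overall LS mean difference uses wᵢ = 1/8 = 0.125.

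**Assumptions (mine, not the documents').** Mean profile 1.0, 1.5, 2.2, 3.0, 3.3, 3.2, 2.6, 2.0 ng/mL at 0, 15, 30, 60, 90, 120, 180 and 240 min; 50 per arm; no site effect. Two benefits are considered:
- Proportional: 35% at every time, averaging 0.35 × 2.35 = 0.8225 ng/mL.
- Meal-only: 0.5 × (mean − 1.0), so fasting is unchanged, averaging 0.5 × 1.35 = 0.675 ng/mL.

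**One case by hand.** Take SD = 0.6 × mean and exchangeable correlation ρ = 0.85. Then wᵢ is proportional to (1/μᵢ)(1/μᵢ − k), with k = ρ/(1 + 7ρ) × Σ(1/μ) = (0.85/6.95) × 3.955 = 0.484. A sample has negative weight whenever 1/μᵢ is below 0.484.
- Weights: 1.18, 0.28, −0.03, −0.11, −0.13, −0.12, −0.09, 0.02.
- Proportional: Σ wᵢμᵢ = (3.955 − 8 × 0.4837)/0.4368 = 0.195. The estimate is 0.35 × 0.195 = 0.07, against a true average of 0.82.
- Meal-only: 0.5 × (0.195 − 1) = −0.40, against a true average of +0.675.

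**Simulation.** The unstructured constant-shift model was fitted, with 500 trials per case. The SDs were 0.6 × mean, 0.6 × √mean, or 1.0 at every time; decaying correlation means 0.9 per 30 min. The overall-test columns give the share of trials significant for benefit / for harm. The equal-weights columns give the share significant for benefit.

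| SD; correlation | Fasting weight | Proportional: overall test | Proportional: equal weights | Meal-only: overall test | Meal-only: equal weights |
|---|---|---|---|---|---|
| ∝ mean; exch. 0.5 | 0.92 | 63% / 0% | 95% | 0% / 30% | 90% |
| ∝ mean; exch. 0.85 | 1.18 | 23% / 1% | 87% | 0% / 100% | 72% |
| ∝ mean; decaying | 1.60 | 51% / 0% | 91% | 0% / 95% | 79% |
| ∝ √mean; exch. 0.5 | 0.66 | 84% / 0% | 100% | 11% / 6% | 100% |
| ∝ √mean; exch. 0.85 | 1.31 | 0% / 50% | 100% | 0% / 100% | 96% |
| ∝ √mean; decaying | 1.49 | 27% / 1% | 100% | 0% / 86% | 99% |
| equal; exch. 0.5 | 0.125 | 100% / 0% | 100% | 98% / 0% | 99% |
| equal; exch. 0.85 | 0.125 | 96% / 0% | 100% | 82% / 1% | 94% |
| equal; decaying | 0.36 | 94% / 0% | 100% | 64% / 0% | 97% |

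With equal SDs no weight is negative. The remaining loss in the exchangeable 0.85 row comes from estimating an unstructured matrix around a misfitting mean, not from unequal true weights. Under compound symmetry every weight is 0.125. Huynh-Feldt with unequal SDs also gave negative weights (approximate calculation).

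**Which structure AIC picks.** In 8 checked runs per case, counting also a constant-shift benefit of 0.4 ng/mL, unstructured was chosen in 140 of 144 runs with unequal SDs. Compound symmetry was chosen in 36 of 48 runs with equal SDs and exchangeable correlation.

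**Where the planned model wins.** For that constant shift, with SD proportional to the mean, it has 96%-100% power against 29%-45% for equal weights.

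**The case against.** The best reply is that the interaction was intended and merely left out of the list. The per-time outputs make no sense without it. SAP 7.5.2.1 and 7.5.2.2 use the same short list for AUC and average daily insulin, yet the addendum shells for those analyses (Tables 14.2.3.x and 14.2.4.X) name the treatment-by-time interaction in their notes. With that term, the overall LS mean difference is already the equally weighted average. I think this is probably the right reading. It does not settle the matter: those shells are not for the time courses, and where the SAP wants the term elsewhere it says so (AST/ALT in 7.6.2.2, weight in 7.6.3).

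A reader might infer that the overall p-value is in effect a fasting test with the stimulated samples counted negatively. The documents do not support that as a fact. They give no SDs or correlations, and AIC may choose compound symmetry. Even in adverse cases some stimulated samples, such as those at 15 or 240 minutes, can keep positive weight.

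A reader might also infer that the log option helps only if the effect is exactly proportional. That is too strong. In log-scale calculations with roughly even variances, all weights were positive (fasting 0.12-0.28). A meal-only benefit was detected in the right direction 46%-97% of the time, against 65%-97% with equal weights, and significant harm was about 0%.

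Finally, stimulated C-peptide has a higher-ranked endpoint of its own, the AUC, tested by t-test as well as by mixed model. Peak C-peptide and unnormalized AUC are reported too. This stands.

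**Conclusion.** The point holds as a specification defect with a conditional consequence. SAP 7.5.2.3 as written cannot produce the per-time results it requires, and it lets a data-driven covariance choice decide what the overall p-value tests.

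If the model is fitted as listed, on the raw scale, with an unstructured or Huynh-Feldt covariance and SDs rising with the mean, the overall test can lose much of its power for a proportional benefit and often reverses a meal-only benefit. The degree depends on assumed profiles, SDs and correlations. In the mildest unequal-SD case above, power for the proportional benefit was still 84%, and the meal-only benefit was mostly missed rather than reversed. With equal variances the weighting problem is absent (exchangeable correlation) or much smaller, with no negative weights (decaying correlation).

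It would be an over-reading to say that a real meal-response benefit would be lost to the trial or reported as harm overall. AUC is tested separately, and since Addendum 3.1 this p-value no longer gates any other endpoint. What is at risk is the reported overall p-value for this one secondary endpoint and for the glucose and insulin courses, which use the same model.

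**What to change.** In SAP 7.5.2.3, add treatment-by-time to each time-course model. Define the overall treatment effect and its p-value as one pre-specified contrast of the eight time-specific LS mean differences, and name that p-value as the analysis of the C-peptide time-course endpoint. Either set of weights would do, if chosen in advance:
- Equal: 0.125 at each time.
- Trapezoidal over 0-240 min: 7.5, 15, 22.5, 30, 30, 45, 60 and 30, each divided by 240. This is close to an unnormalized mean AUC; equal weights give more influence to the early samples.

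The work is a few words in the SAP and one estimate statement per model. It also reconciles the section with its own per-time outputs. The statistical cost is seven more parameters per model ((8 − 1) × (2 − 1) = 7) and less power if the true effect is a constant shift.
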